### 10.4 Adaptive Design and Sample Size Considerations

Available literature does not provide a precise estimate of the expected anastomotic leak rate in the control group or in the treatment group. As previously described, anastomotic leak is reported to occur in a wide range of 3-20% of the time in colorectal surgery and the risk increases for lower anastomoses. In the limited prior experience with the PINPOINT PILLAR II study (n=139 subjects) the anastomotic leak rate was 1.4%.

Given the limited knowledge of control incidence and the treatment effect size, the PILLAR III study will employ an adaptive design with a mid-trial sample size re-assessment. The planned sample size is  $N = 800$ , with possible early stopping for efficacy or futility at an interim analysis at  $N = 450$ . The planned total of 800 subjects will provide >80% power to test the one-sided hypothesis of superiority for treatment over control in leak rate at the 0.025 significance level if the true leak rates  $p_c$  and  $p_t$  are 12.5% and 6.25% (a 50% relative reduction), assuming a two-look group sequential analysis plan (with Pocock alpha-spending bounds and analyses at 450 and 800). If the trial does not stop at  $N = 450$ , sample size will be assessed at that time and possibly increased up to a maximum of 1000 subjects, using the method of Chen et al. and described in Mehta and Pocock.

For the primary objective, the following analysis plan will be used After  $N = 450$  subjects have been enrolled, randomized and treated and the primary outcomes observed. The primary objective null hypothesis will be tested against the one-sided alternative hypothesis above. If  $p < 0.0169$  (as determined by the Pocock alpha spending function), the null hypothesis will be rejected, whereas if  $p \geq 0.4$ , the trial will be considered futile. However, if  $0.0169 \leq p < 0.4$  an assessment of whether to increase the sample size above the planned 800 subjects will be made in accordance with the “promising zone” method of Mehta and Pocock. If the conditional power (CP) at  $N = 800$  subjects based on the available data at the time of the interim analysis is less than 0.5 or at least 0.8, enrollment will continue to 800 subjects and the final analysis will be conducted. Alternatively, if  $0.5 \leq CP < 0.8$ , the sample size will be re-estimated in accordance with the Mehta and Pocock method for sample size re-estimation up to a maximum of 1000 subjects. (The recalculated sample size cannot be less than 800 subjects based on the interim analysis.) The final sample size is calculated by determining the added sample size needed to achieve the target conditional power of 80% given the data at the time of the interim analysis, subject to a maximum of 1000 subjects. This method guarantees control of the type I error while still allowing standard inferential methods of analysis.

**10.5 The planned sample size 800 . is based on the following rationale: If the true leak rates  $p_c$  and  $p_t$  are 12.5% and 6.25% (a 50% relative reduction), respectively, then PASS 13 indicates that , a two-look group sequential analysis plan (with Pocock alpha-spending bounds and analyses at 450 and 800) achieves 81.6% power to reject the null hypothesis at a one-sided significance level of 0.025. Study Populations for Analysis**

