### 10.3 Statistical Analysis

Analysis of these hypotheses will be conducted using a z-test (i.e., normal approximation to the binomial distribution, using a pooled variance estimate and without continuity correction), using a (one-sided) significance level of 0.025.

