4.1 General

Categorical variables will be summarized with the number and percent of subjects in each group. Continuous variables will be summarized with the mean, standard deviation, median, minimum, and maximum values. 95% confidence intervals will be calculated for the primary and secondary endpoints.

All data collected in the CRF will be presented in the listings.

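### If the stop at 450 in Protocol 10.4 still applies, the unadjusted 95% CI in SAP 4.1 does not match the design, and the ordinary estimate after an efficacy stop is biased upwards.

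*Protocol*

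**What the plan says.** Protocol 10.4 plans 800 subjects with one interim analysis at 450. The trial stops for efficacy if the one-sided p is below 0.0169 and for futility if it is 0.4 or more. Otherwise, conditional power from 0.5 up to 0.8 leads to re-estimation, to at most 1000. The design is described as "with Pocock alpha-spending bounds and analyses at 450 and 800". The paragraph on the re-estimation rule ends: "This method guarantees control of the type I error while still allowing standard inferential methods of analysis".

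Protocol 10.3 sets the primary analysis as a z-test "using a pooled variance estimate and without continuity correction", "using a (one-sided) significance level of 0.025". No separate critical value is given for the final look. Protocol 10.2 estimates each leak rate as a raw proportion, and Protocol section 10 mentions 95% CIs only for the secondary objectives.

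The CI for the primary endpoint is in SAP 4.1: "95% confidence intervals will be calculated for the primary and secondary endpoints". Its form is not given. The SAP contains no interim look, Pocock bound, futility rule or re-estimation. SAP 3.1 and 3.3 take everyone enrolled through March 31, 2017 as the sample, and SAP 6.1 runs one z-test at 0.025. Neither document specifies an estimate or interval adjusted for the sequential design.

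**The concern.** Control of type I error is a property of the decision rule. It does not carry over to the estimate and interval computed when the trial stops. A trial that can stop at 450 because the observed difference is large will, when it does so, tend to report a difference larger than the true one. An ordinary 95% CI uses z=1.96 at whichever look ends the trial, whereas the test needs about 2.12 at 450 and 2.22 at the end. The interval therefore has two chances to exclude zero, each at a looser threshold than the test.

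Two results are at stake: the reported size of the leak reduction after an early success, and a final report in which the CI excludes zero although the primary test has failed.

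**Working it through.** **Inputs.** One-sided alpha 0.025 and pooled z-test (Protocol 10.3). Looks at 450 and 800, interim p<0.0169, futility p>=0.4, re-estimation to at most 1000 (10.4). 1:1 allocation (5.1), so 225 per arm at the interim and 400 per arm at 800. Leak rates that "are 12.5% and 6.25% (a 50% relative reduction), assuming a two-look group sequential analysis plan" (10.4). No dropout is stated in the sample size section; it is taken as zero.

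**1. Reproduce the plan's figures.**
- Information fraction: 450/800 = 0.5625.
- Pocock-type spending: 0.025 × ln(1 + (e−1) × 0.5625) = 0.0169, z = 2.122. This matches 10.4.
- Final bound: solving for overall alpha 0.025 with correlation √0.5625 = 0.75 gives z = 2.220, one-sided p = 0.0132. The Protocol does not state it.
- Power: pooled rate 0.09375, so 2 × 0.09375 × 0.90625 = 0.1699. Drift is 0.0625/√(0.1699/225) = 2.27 at 450 and 0.0625/√(0.1699/400) = 3.03 at 800. With bounds 2.122 and 2.220 the bivariate normal gives 81.6%, as in the Protocol, which says the plan "achieves 81.6% power to reject the null hypothesis at a one-sided significance level of 0.025".

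**2. Estimate after an efficacy stop.** Two binomials of 225 were enumerated exactly, conditional on p<0.0169. At 12.5% vs 6.25% the chance of this stop is 57%. The mean observed difference given the stop is 8.11 points, and 8.11/6.25 = 1.30, or +30%. On the relative scale the mean observed reduction is 59.5% against a true 50%, or +19%. Over all trials the mean difference is 6.67 points, or +7%.

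The conditional figure on the absolute scale depends on the true rates:

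| True rates | Overstatement given an efficacy stop |
|---|---|
| 12.5% vs 5% | +13% |
| 15% vs 7.5% | +21% |
| 12.5% vs 6.25% | +30% |
| 10% vs 5% | +42% |
| 12.5% vs 7.5% | +57% |
| 8% vs 4% | +57% |

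**3. Behaviour of the interval.** The whole design was simulated (at least 400,000 trials per scenario): binomial counts, pooled z-tests, both stopping rules, and conditional power under the observed trend,

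CP(n) = 1 − Φ[(2.220√n − z₁√n₁)/√(n − n₁) − (z₁/√n₁)√(n − n₁)],

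with n and n₁ per arm. If CP(400) lies from 0.5 up to 0.8, n rises until CP reaches 0.8, to at most 500. The interval is difference ± 1.96 × unpooled standard error.

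| Quantity | Unadjusted 95% CI | Repeated CI (2.122 / 2.220) |
|---|---|---|
| 12.5% in both arms: CI excludes zero in favour of imaging | 3.4% | 2.5% |
| 12.5% vs 6.25%: coverage | 93.9% | 95.9% |
| 12.5% vs 6.25%: CI excludes zero, test fails | 4.4% | below 0.1% |
| 12.5% vs 8.5%: CI excludes zero, test fails | 7.6% | 0.2% |

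All mismatches arise at the final look, where the one-sided p lies between 0.0132 and 0.025. At 12.5% vs 6.25% they are about 11% of the trials that reach that look. No rejection came with a CI that included zero. The test keeps its level: the rejection rate with no effect was 2.5%.

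**The case against.** The strongest objection is that the point joins two documents that describe different trials. The stop at 450 is only in the Protocol; the CI for the primary endpoint is only in the SAP, which has one analysis. Under the SAP alone neither the bias nor the mismatch arises. This limits the point but does not remove it. The SAP's revision history says it is based on Protocol version 1.4, and the SAP neither withdraws the adaptive design nor says that no interim look was taken.

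The mismatch also depends on a final bound that the Protocol does not state. If the final look used 0.025, as 10.3 can be read, test and CI would broadly agree, but overall type I error would be 3.4%.

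Several stronger inferences fail:
- **The 30% as a general figure.** It applies to the absolute difference, given an efficacy stop, at the design rates. Much of it comes from conditioning on significance in 450 subjects: a fixed trial of 450, looked at only when significant at 0.025, averages 7.87 points (+26%).
- **A CI that contradicts the test at an early stop.** It cannot in this design, since p<0.0169 is stricter than 0.025. Coverage among efficacy stops at the design rates is 96.0%.
- **A large loss of coverage.** A fixed-sample Wald interval covers 94.9% at these rates, so the loss is about one point.
- **Labeling use of the primary effect size.** Protocol 10.7 and SAP 6.2 make that statement about the secondary objectives.
- **A broad claim in the 10.4 sentence.** It closes the re-estimation rule and does not mention estimates or intervals. Limiting it to the test is a clarification.

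**Conclusion.** The point holds conditionally. If the Protocol 10.4 design governs, the unadjusted 95% CI does not correspond to the test: it wrongly favours imaging in 3.4% rather than 2.5% of trials with no effect, and at the design rates 4.4% of trials would end with a CI excluding zero beside a failed test. The more visible consequence is the estimate after an efficacy stop, the most likely single outcome at the design rates (57%), which averages 8.1 points against 6.25. If the trial had one analysis, as the SAP describes, fixed-sample intervals are correct and none of this applies.

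The figures assume a Wald CI for the difference, a final z of 2.220, conditional power under the observed trend and no dropout. The hypothesis test is not in question if that final bound is used. This should be corrected, but it does not threaten the validity of the trial.

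**What to change.** 1. Reconcile Protocol 10.4 with SAP 3.1 and 3.3. If no interim look was taken, say so in the SAP and keep fixed-sample 95% CIs.
2. If the sequential design applies, limit the closing sentence on the re-estimation rule in 10.4 to the hypothesis test, and state the final bound (z=2.220, one-sided p=0.0132).
3. In SAP 4.1 and 6.1, report the difference in leak rates with repeated CIs: z=2.122 if the trial ends at 450 and z=2.220 at the final look (nominal 96.6% and 97.4%). Name the standard error used.
4. For a stop at 450, either label the ordinary estimate as subject to early-stopping bias or add a bias-adjusted estimate, for example a mean-bias-adjusted or conditional one. A median-unbiased estimate under stage-wise ordering equals the ordinary estimate at a first-look stop and would not help. A repeated CI leaves the point estimate unchanged.

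The cost is wording, a little programming and a slightly wider interval: by a factor of 2.122/1.96 = 1.08 at 450 and 2.220/1.96 = 1.13 at the end. An adjusted estimate after an early stop would be less favourable.

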#### 10.5.1 Modified Intent-to-Treat (mITT)

The mITT analysis population includes all randomized subjects in whom a low anterior resection surgical procedure is initiated or at least one injection with ICG was performed. All subjects meeting these criteria are included in the mITT population, regardless of whether or not they received the planned open, or minimally invasive surgical intervention or NIR fluorescence imaging assessment using the PINPOINT or SPY Elite device. Subjects who have the surgical resection procedure aborted due to circumstances such as a higher stage cancer than initially anticipated will not be included in the mITT population. Subjects will be analyzed according to their randomized group assignment. The mITT population is the analysis population for both the primary and secondary endpoints.

#### 10.5.2 As-Treated (AT)

The As-Treated (AT) analysis population includes all randomized subjects in whom the intended open, or minimally invasive low anterior resection surgical procedure and, if assigned to the PERFUSION arm, PINPOINT or SPY Elite NIR fluorescence imaging with at least one perfusion assessment using ICG was successfully performed. Subjects in whom the intended surgical procedure is not performed or imaging with PINPOINT or SPY Elite was not successful are excluded from the AT population. mITT subjects not included in the AT population will be followed in the same manner as mITT subjects who do meet AT population inclusion criteria. Subjects will be analyzed according to the treatment actually received.

The AT population will be used for a secondary analysis of the primary endpoint.

### 10.5.3 Per-protocol (PP)

The Per-protocol (PP) population will consist of all AT subjects that: [1] meet critical study eligibility criteria; [2] have no significant protocol deviations; and [3] have evaluable assessment for the primary study endpoint.

The PP population will be used for subset analysis of the primary endpoints.

## 10.6 Safety (S)

The safety analysis population includes all randomized subjects. Secondary safety endpoints including the summary of adverse events in the trial will be analyzed using this analysis population, divided into groups according to actual use or non-use of PINPOINT and SPY Elite.

## 10.7 Secondary Objectives

The planned secondary objectives are listed below; they will be formally analyzed only once (at the interim analysis if the primary objective is passed at that time, or at the final analysis if the primary objective is not passed at the interim analysis). Data from these secondary objectives will not be included in the sample size re-assessment that occurs at the time of the interim analysis. The following objectives are intended to support product labeling. They will be tested in sequential fashion. I.e., if and only if the primary objective passes according to the criteria in Section 10.5 (which has a type I error rate of 2.5%), testing will proceed to the first secondary objective below (proportion of PERFUSION arm subjects in whom the PINPOINT or SPY Elite system provided sufficient visualization for assessment of blood flow and related tissue perfusion during the procedure). If and only if that objective passes, testing will proceed to the second secondary objective (incidence of abscess requiring surgical management). The standard for “passing” the secondary objectives will be a p-value less than 0.025 one sided.

To evaluate the ability of the PINPOINT or SPY Elite system to provide sufficient visualization for assessment of blood flow and related tissue perfusion during the procedure.

The statistical threshold for study success will be sufficient visualization for assessment of blood flow and related tissue perfusion in greater than 90% of subjects. Letting  $p_t$  represent the PERFUSION-group proportion of subjects for whom there was sufficient visualization for assessment of blood flow and related tissue perfusion, the following hypotheses will be tested:

H0:  $p_t \leq 0.9$

H1:  $p_t > 0.9$

The statistical test will be a one-sided exact binomial test of proportions. Descriptive statistics and 95% confidence intervals will be calculated for  $p_t$ .

To evaluate the effectiveness of assessing perfusion of colon and rectal tissue using PINPOINT or SPY Elite in reducing the incidence of post-operative abscess requiring surgical management.

Letting  $p_t$  and  $p_c$  respectively represent the treatment-group and control-group incidence of post-operative abscess requiring surgical management, the following hypotheses will be tested:

$$H_0: p_t = p_c$$

$$H_1: p_t < p_c$$

The statistical test will be a z-test using pooled variance estimate and no continuity correction. In the case of small counts, an exact procedure will be used. Descriptive statistics and 95% confidence intervals will be calculated for  $p_t$ ,  $p_c$ , and  $(p_t - p_c)$ .

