
Study Design
 
This is a randomized, controlled, parallel, multicenter study to determine the reduction in post-operative anastomotic leak rate in low anterior resection (LAR) procedures where colon and rectal tissue perfusion is evaluated using PINPOINT or SPY Elite as an adjunct to standard surgical practice compared to surgical procedures performed according to standard surgical practice alone. The study is a two-stage adaptive design that allows a mid-trial reassessment of sample size. Therefore, a minimum of 450 and a maximum of 1000 subjects will be enrolled at up to 40 centers in North America. Prior to enrolling study subjects, participating surgeons at each center will be trained to perform perfusion assessment with PINPOINT.
 
Screening:
 
Patients scheduled for an open, or minimally invasive low anterior resection for a rectal or rectosigmoid neoplasm with curative intent with a planned anastomosis located 10 cm or less from the anal verge will be evaluated at baseline to determine if they meet the inclusion/exclusion criteria of the protocol. Subjects will be assessed to determine overall health status, including demographics, vital signs and predictive factors that may influence surgical outcomes. Eligible patients who provide informed consent will be considered for inclusion into the study.
 
Day 0:
 
During anesthesia, subjects will be randomized (1:1) to either the PERFUSION (PFN) Arm or the STANDARD (STD) Arm. Subjects in each arm will be randomized according to an independently generated randomization scheme to receive either perfusion assessment with PINPOINT and/or SPY Elite during the surgical procedure or to receive the standard of care procedure. Randomization will be stratified by site and by whether or not the patient received prior neoadjuvant therapy.
 
Subjects in the PFN Arm will undergo a LAR according to the surgeon's standard practice with the addition of intraoperative imaging using PINPOINT and/or SPY Elite NIR fluorescence imaging to assess colon and rectal tissue perfusion during the following steps of the procedure:

- perfusion of proximal transection margin after IMA ligation; prior to bowel transection
- perfusion of the mucosal aspect of the completed anastomosis (with the exception of hand sewn coloanal anastomoses which will involve assessment of the mucosal aspect of the proximal colon only)

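### Under the protocol's two-look plan, testing abscess at the full one-sided 0.025 at whichever look the primary passes does not strictly hold its error rate at 2.5%

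*Protocol*

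**What the plan says.** Protocol Section 10.4 plans a two-look design "with Pocock alpha-spending bounds and analyses at 450 and 800". The interim efficacy threshold is a one-sided p-value below 0.0169, "as determined by the Pocock alpha spending function". At an interim p-value of 0.4 or more, "the trial will be considered futile". Between these thresholds the trial continues to 800 subjects, or up to 1000 after re-estimation.

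Section 10.7 sets a fixed sequence: leak, then visualization, then abscess requiring surgical management. On timing it says "they will be formally analyzed only once (at the interim analysis if the primary objective is passed at that time", and otherwise at the final analysis. The criterion for passing "the secondary objectives will be a p-value less than 0.025 one sided", with no distinction between looks. The Protocol Summary and SAP Section 6.2 repeat that level. Section 10.7 also says these objectives are meant to support labeling.

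The Protocol Summary, Section 3.1 and Section 9.4 let the surgeon classify an abscess thought to be related to the anastomosis as a leak. Section 9.4 goes further: an adjacent abscess that contains air counts as a leak.

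SAP Sections 3.1 and 3.3 take everyone enrolled through March 31, 2017 as the sample and describe no interim look.

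**The concern.** In a trial with one analysis, a fixed sequence at full alpha controls the error rate of every test in it. With two looks that argument no longer covers a secondary endpoint correlated with the primary. A chance-favourable abscess result at 450 makes it more likely that the leak comparison passes at 450, and abscess is then tested there at the full 0.025. If the leak comparison misses at 450 and passes later, abscess is tested at the final analysis, again at the full 0.025. Each trial contains only one abscess test, but the look at which it is made depends partly on the abscess data.

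At stake is whether a claim intended for labeling meets the 2.5% standard that the protocol sets for it.

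**Working it through.** **Inputs from the documents.** Looks at 450 and 800, so the information fraction is t = 450/800 = 0.5625. One-sided alpha is 0.025, futility is at interim p ≥ 0.4, and allocation is 1:1. The planning leak rates "are 12.5% and 6.25% (a 50% relative reduction").

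**Input not in the documents.** The correlation rho between the leak and abscess statistics. It is assumed and varied.

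**1. Reproduce the plan's own figures.**
- Pocock-type spending at the interim: 0.025 × ln(1 + (e − 1) × 0.5625) = 0.0169, as stated; c1 = 2.122.
- Final bound, using correlation √0.5625 = 0.75 between looks: c2 = 2.220, nominal one-sided p = 0.0132.
- Planning drift at 800: the pooled leak rate is (12.5% + 6.25%)/2 = 9.375%, so 0.0625 / √(0.09375 × 0.90625 × 2/400) = 3.03.
- Power with pooled variance and no futility stop is 0.816, matching the protocol's statement that the design "achieves 81.6% power to reject the null hypothesis at a one-sided significance level of 0.025". The chance of passing at the interim is 0.560.

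**2. Abscess error rate.** Let Z1, Z2 be the leak statistics and Y1, Y2 the abscess statistics at the two looks, with no true abscess effect. The error rate is

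P(Z1 ≥ 2.122, Y1 ≥ 1.96) + P(0.253 ≤ Z1 < 2.122, Z2 ≥ 2.220, Y2 ≥ 1.96).

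The visualization step is taken as passed, which is the unfavourable case. In practice it would filter little: it needs 212 of 225 or 372 of 400 successes, and Section 1.2 reports 98.6% successful imaging in the earlier study.

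| rho | Worst case over leak effects | At 12.5% vs 6.25% | No leak effect |
|---|---|---|---|
| 0 | 2.50% | 2.04% | 0.06% |
| 0.2 | 2.53% | 2.39% | 0.17% |
| 0.3 | 2.56% | 2.52% | 0.26% |
| 0.5 | 2.66% | 2.65% | 0.52% |
| 0.7 | 2.83% | 2.62% | 0.95% |

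Simulated re-estimation up to 1000 subjects changes little: 2.68% at rho 0.5 and 2.88% at rho 0.7.

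**3. Which rho is plausible.** Assume every surgically managed abscess is also a leak, with abscess rate a and pooled leak rate 9.375%. Then rho = √[a(1 − 0.09375) / (0.09375(1 − a))]. Assumed abscess rates of 1%, 3% and 5% give 0.31, 0.55 and 0.71. Less overlap lowers these values.

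**4. Binary counts instead of normal theory.** Two looks with the futility stop, no re-estimation, z-test at 0.025, no abscess effect, 1 million runs per scenario.

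| Leak rates | Overlap | Abscess 1% | 3% | 5% |
|---|---|---|---|---|
| 12.5% vs 6.25% | 100% | 2.2% | 2.6% | 2.5% |
| 12.5% vs 6.25% | 80% | 2.2% | 2.6% | 2.5% |

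The highest value in any scenario tried was about 3.0% (leak 8% vs 5.5%, abscess 5%, full overlap).

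**5. With levels by look.** With Pocock-type levels for abscess (0.0169 and 0.0132), the maximum error is 1.70%, 1.74%, 1.82% and 2.03% at rho 0.3, 0.5, 0.7 and 0.9, and 2.50% at rho 1. With O'Brien-Fleming-type levels (about 0.0028 and 0.0241), the simulated error was at or below 1.2% in every scenario run.

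**The case against.** The strongest reply is that the excess may not arise at all.

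- **Exact test.** Section 10.7 calls for an exact procedure when counts are small. At 450 subjects, abscess rates of 1% to 3% give 225 × 0.01 = 2.25 to 225 × 0.03 = 6.75 events per arm, so it could well apply. With Fisher's exact test at 0.025, the simulated error was 0.4% to 1.9% in every scenario. This stands, but the protocol does not define small, so the protection is not assured.
- **SAP.** With a single analysis, abscess can be declared only if its one p-value is below 0.025, so its error is at most 2.5%. This also stands. The protocol still carries the two-look rule, and the documents do not say which governs.
- **Over-correction.** Pocock-type levels leave the error at 1.7% to 1.8% for rho 0.3 to 0.7, giving up power to remove a small excess. That is fair, and it is a reason not to prescribe one particular set of levels.

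Two stronger readings are tempting. A reader might infer that the error rate always exceeds 2.5%. It does not: it is at or below 2.5% with no leak effect, and at the planning effect with rho of 0.2 or less. A reader might also take the normal-theory limit of about 4.0% as rho approaches 1 as the size of the problem. For two binary endpoints rho = 1 means the same event, so no abscess effect then means no leak effect, where the rate is at or below 2.5%.

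**Conclusion.** The point holds in a limited form. Under the protocol's two-look plan the abscess test is not strictly controlled at 2.5%. For an assumed correlation of 0.3 to 0.7, the worst-case excess over leak effects is about 0.1 to 0.3 percentage points in normal theory. With simulated counts and the z-test, the rate at the planning effect lies on either side of 2.5%, and it reached about 3.0% in the least favourable scenario tried.

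This rests on three conditions: the interim efficacy look is carried out, abscess and leak are positively correlated, and the z-test is used. The leak definition supports the second condition but gives no value. The visualization test is not affected if its result is unrelated to the leak result: at rho 0 the rate never exceeds 2.5%.

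**What to change.** In Section 10.7 and the Protocol Summary, give the abscess test its own group-sequential levels by look. Two options are:

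- Pocock-type: 0.0169 at 450 and 0.0132 at the final analysis.
- O'Brien-Fleming-type: about 0.0028 and 0.0241. This keeps most of the alpha for the final look but is strict at the interim, where the primary passes about 56% of the time at the planning effect.

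Visualization may stay at 0.025. If the SAP's single analysis with no interim efficacy look governs, state that in the protocol and keep 0.025 for abscess, tied to that statement.

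The change is about one sentence in each place. It costs some power for the abscess objective only; the primary test and the sample size are unaffected.
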